10.4 Data Analysis

Descriptive statistics, including mean, median, standard deviations and ranges for all continuous measures will be tabulated and reported. Percentages and frequencies for all categorical measures will also be presented. For time to event outcomes, the median and 25% and 75% percentiles will be summarized with associated 95% confidence intervals. All statistical analyses will be performed using SAS 9.1 or higher. Demographics and Baseline Characteristics

Demographic and baseline disease characteristics will be summarized. Data to be tabulated will include demographic features such as age, sex and race, as well as disease-specific characteristics.

The number and percentages of patients enrolled, treated, completing the treatment/study and withdrawn from treatment/study for any reasons will be summarized.

10.4.1 Efficacy Analysis

Efficacy analyses will be reported for FAS population. Additionally, the ORR, Clinical Benefit Rate (CBR), and PFS will be summarized for the Evaluable Population. The following outcomes will be used to evaluate the clinical benefit of the study treatment:

- Overall Response Rate (ORR) is defined as the proportion of patients with confirmed complete response (CR) or partial response (PR (i.e. 2 CRs or PRs at least 4 weeks apart) according to RECIST v1.1 criteria.
- Clinical Benefit Rate (CBR) is defined as the proportion of patients with CR, PR or stable disease (SD) (≥ 6 cycles) according to RECIST v1.1 criteria.

CONFIDENTIAL

- For ORR and CBR, patients without a post-baseline tumor assessment will be classed as not evaluable (NE) and considered as non-responders.
- Progression-free Survival (PFS) is defined as the time from the first day of study drug administration (Day 1) to disease progression as defined by RECIST v1.1 criteria, or death on study. Patients who are alive and free from disease progression will be censored at the date of last tumor assessment.

For ORR and CBR, the estimates and the associated 95% CI based on the Clopper-Pearson method will be calculated. For PFS, Kaplan-Meier curves will be generated and the median time to event and the associated 95% CI be provided.

Safety Analysis

Safety will be assessed through the analysis of the reported incidence of treatment-emergent AEs. Treatment-emergent AEs are those with an onset on or after the initiation of therapy, and will be graded according to NCI CTCAE v4.03. A copy of CTCAE scoring system may be downloaded from: https://evs.nci.nih.gov/ftp1/CTCAE/CTCAE.

The AEs will be coded using Medical Dictionary for Regulatory Activities (MedDRA), and summarized using system organ class and preferred term for all patients in the Safety Population. In addition, summaries of serious adverse events (SAEs), AEs leading to treatment discontinuation, AEs by maximum NCI CTCAE grade, and AEs related to study treatment will also be presented.

Other safety endpoints including changes in laboratory results, vital signs and ECG findings will be summarized for the safety population. Summaries of laboratory abnormalities based on maximum CTCAE grading will also be produced.

10.5 Analysis Time Points

10.5.1 Final Analysis

The final analysis of the study will occur when all patients progress or, for any patients with a sustained response or stable disease, a minimum of 3 treatment cycles have been completed.

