Appendix D: Study assessment table

Fresh biopsy collection and footnote "i" has been deleted to reflect the changes.

GI 195 PROTOCOL SYNOPSIS

Title of Study:	Phase II Study of Carfilzomib for the Treatment of Patients with Advanced Neuroendocrine Cancers
SCRI Innovations Study Number:	GI 195
Sponsor:	SCRI Development Innovations, LLC. Nashville, TN
Study Duration:	The total duration of the study is planned to be 24 months. Phase of Study: II
Study Centers:	This study will be conducted at multiple sites.
Number of Patients:	Up to 62 patients are planned to be enrolled in this study.
Objectives:	 Primary Objective The primary objective of this study is to: To evaluate the overall response rate (ORR) of patients with advanced neuroendocrine tumors treated with carfilzomib.
	 Secondary Objectives The secondary objectives of this study are: To evaluate the disease control rate (DCR) in patients with advanced neuroendocrine cancers treated with carfilzomib.
	• To evaluate the progression free survival (PFS) of patients with advanced neuroendocrine cancers treated with carfilzomib.
	• To further evaluate toxicities associated with this regimen.
	Exploratory Objective The exploratory objective of this study is:
	• To determine the status of gene mutation and protein expression by immunohistochemistry (IHC) on the tumor samples to explore the correlation with the response to treatment will be done.
Study Design:	This Phase II open-label, non-randomized clinical study will be conducted by participating sites in the Sarah Cannon Research Institute network. This study will evaluate the use of carfilzomib for patients with advanced neuroendocrine tumors. Patients will receive treatment by intravenous (IV) infusion over 30 minutes on days 1, 2, 8, 9, 15, and 16 of each cycle. Cycles are 28 days in length. Patients will be evaluated for response to treatment every 3 cycles; responding and/or stable patients will continue treatment, with re-evaluations every 3 cycles, unless tumor progression or intolerable toxicity occurs. Response to therapy will be assigned using RECIST v1.1 criteria.
Study Drugs, Doses, and Modes of Administration:	Carfilzomib will be administered as IV infusion. Patients will receive 20 mg/m ² on Days 1 and 2 of Cycle 1. Thereafter, patients will receive 56 mg/m ² on Days 8, 9, 15 and 16. Starting from Cycle 2 patients will receive 56 mg/m ² on Days 1, 2, 8, 9, 15 and 16.

GI 195 PROTOCOL SYNOPSIS

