10. STATISTICAL CONSIDERATIONS

10.1 Statistical Design

This is a multicenter, Phase II study of carfilzomib for the treatment of patients with advanced neuroendocrine cancers.

Demographic data and baseline disease characteristics will be summarized using appropriate descriptive statistics (e.g., mean, median, standard deviation or percentages and frequency counts).

The primary endpoint, ORR, will be determined using RECIST v1.1 criteria. The median and 25% and 75% percentiles for PFS will be summarized with associated 95% CI, and the distribution of PFS will be presented graphically using the Kaplan-Meier approach. Progression-free survival will be evaluated six and 12 months after the last patient is enrolled on the trial.

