10.5.2 Planned Interim Analysis

No interim analyses are planned. Interim results may be presented at congress prior to final study report, if applicable. The design follows that of Simon et al. 1989. If < 2 of the initial 23 patients enrolled in the study fail to achieve a response, the study will be stopped and the remaining 33 additional patients will not be enrolled. Patients will be evaluated for response to treatment every 3 cycles. Patients will be removed from treatment at the time of disease progression. Patients demonstrating an extended period of stable disease will be considered non-responders after 12 cycles of treatment.

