This study will be registered on ClinicalTrials.gov by the sponsor, SCRI Development Innovations within 21 days of the enrollment of the first patient as required by the Food And Drug Administration Amendments Act of 2007. Updates and changes will be submitted to ClinicalTrials.gov in compliance with regulations. The Primary Completion Date for this study will be the date upon which the last patient undergoes an assessment for response [the primary outcome variable is Overall Response Rate (ORR) which is defined as the proportion of patients with confirmed complete response (CR) or partial response (PR) according to RECIST v1.1 criteria]. Patients will be evaluated for response every 3 cycles. Patients demonstrating an extended period of stable disease will be considered non-responders after 12 cycles of treatment.

CONFIDENTIAL

STUDY DRUG(S): CARFILZOMIB AMENDMENT 2 DATE: 25 FEBRUARY 2015

Study results will be posted on ClinicalTrials.gov within 12 months of the Primary Completion Date

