- n Patients who discontinue study treatment prior to the occurrence of disease progression will be followed every 3 months (±1 month) from the date of last dose of study drug until disease progression. PFS will be evaluated for this trial 6 and 12 months after the last patient is enrolled. No follow up will be done for survival or if the patient starts a subsequent therapy.

STUDY DRUG(S): CARFILZOMIB AMENDMENT 2 DATE: 25 FEBRUARY 2015 CONFIDENTIAL SCRI INNOVATIONS STUDY NUMBER: GI 195 VERSION 3.0

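### The 3-cycle minimum before the final analysis (10.5.1) is shorter than the follow-up that CBR and confirmed ORR (10.4.1) require

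*Combined protocol and SAP*

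**What the plan says.** **Trigger.** Section 10.5.1 sets the final analysis at progression of all patients or, "for any patients with a sustained response or stable disease, a minimum of 3 treatment cycles have been completed". *Sustained* is not defined.

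**Endpoints.** Section 10.4.1 defines ORR by confirmed response, that is "2 CRs or PRs at least 4 weeks apart". It defines CBR as the "proportion of patients with CR, PR or stable disease (SD) (≥ 6 cycles"). Its one rule for incomplete data makes patients with no post-baseline assessment non-responders. It says nothing about a response not yet confirmed, or stable disease still short of 6 cycles, at the cut-off.

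**Scans.** Sections 5 and 7.4 and Appendix D give 28-day cycles with imaging every 3 cycles. Appendix D lists no separate 4-week confirmatory scan. Patients who stop treatment before progression are scanned at the end of treatment and followed about every 3 months (7.6.1).

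**Other timing statements.**
- Section 10.1: "Progression-free survival will be evaluated six and 12 months after the last patient is enrolled on the trial". Appendix D, footnote n, repeats this for PFS.
- Section 12: "The Primary Completion Date for this study will be the date upon which the last patient undergoes an assessment for response". It does not say which assessment.
- Section 10.5.2, repeated in section 12: "Patients demonstrating an extended period of stable disease will be considered non-responders after 12 cycles of treatment".
- Synopsis: "The total duration of the study is planned to be 24 months".

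**The concern.** A minimum follow-up rule should ensure that every patient can be classified on every endpoint before the data are cut. This one does not. At day 84 a patient in stable disease has not had time to count towards CBR. A patient whose first response appears on the cycle-3 scan has not had time to confirm it. Both would be scored as failures because of the calendar.

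The error runs in one direction. ORR and CBR are biased downward, so the risk is missing an active drug rather than a false claim of activity. ORR matters most because section 10.2 decides the trial on at least 6 responses in 56, where one or two uncounted responses can change the result. CBR is descriptive. It is taken here as the analysis of the disease control rate objective in 2.2, a link the documents do not state.

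**Working it through.** **1. The plan's own design (10.2).** Stage 1 has 23 patients and continues with at least 2 responses. Success is at least 6 responses in 56. With response rate p:

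P(success) = Σ over x = 2 to 23 of P[Bin(23, p) = x] × P[Bin(33, p) ≥ max(0, 6 − x)]

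This gives 0.8003 at p = 0.15 and 0.04996 at p = 0.05. The stated power of 80% and type I error of 0.05 are reproduced and are not in question.

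**2. Follow-up guaranteed and needed** (days from first dose, no dose delays)

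| Requirement | Days |
|---|---|
| 10.5.1 floor | 3 × 28 = 84 |
| Response at cycle 3, confirmed by an unscheduled 4-week rescan | 84 + 28 = 112 |
| Response at cycle 3, confirmed at the next scheduled scan | 6 × 28 = 168 |
| Stable disease ≥ 6 cycles | 6 × 28 = 168 |
| 12-cycle rule (10.5.2) | 12 × 28 = 336 |

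The floor is 84 days short for CBR. For ORR it is 28 days short, or 84 on the scan schedule.

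**3. Patients affected (assumptions).** The documents give no accrual rate. The planned 24 months less the 12-month PFS evaluation leaves 730 − 365 = 365 days for accrual. An assumed 84-day pause after stage 1 would leave 281 days (9.2 months). So 9 to 12 months is used, about 274 to 365 days. Further assumptions are uniform accrual, first dose on the enrolment date, stage 1 fully followed, and a cut exactly at the floor. The number affected is k = 56 × gap ÷ accrual time:
- Gap 84 days: 56 × 84 ÷ 274 ≈ 17, or 56 × 84 ÷ 365 ≈ 13. As shares, 17/56 = 30% and 13/56 = 23%.
- Gap 28 days: 56 × 28 ÷ 274 ≈ 6, or 56 × 28 ÷ 365 ≈ 4.

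**4. Effect on the ORR decision.** All k patients fall in stage 2. Where none of their responses can be confirmed, Bin(33, p) in step 1 becomes Bin(33 − k, p). Where *sustained* means confirmed and a share f of responses first appears at cycle 6, the last k patients respond with probability p × (1 − f).

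| Case, cut at the floor | k (9 / 12 months) | Power at 0.15 | Type I error |
|---|---|---|---|
| Complete data | 0 | 0.800 | 0.050 |
| 4-week rescans | 6 / 4 | 0.739 / 0.763 | 0.033 / 0.039 |
| Confirmation waits for cycle 6 (worst case) | 17 / 13 | 0.533 / 0.623 | 0.012 / 0.018 |
| *Sustained* = confirmed, f = 0.25 | 17 / 13 | 0.758 / 0.770 | lower |
| *Sustained* = confirmed, f = 0.50 | 17 / 13 | 0.701 / 0.731 | lower |
| *Sustained* = confirmed, all responses by cycle 3 | 0 | 0.800 | 0.050 |

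The values of f are illustrative; the documents give none.

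**5. The two dates already planned for PFS.**
- *6 months (day 183).* This passes day 168 by 15 days, so both definitions are met for a cycle-3 response. Section 6 tolerates a dose delay of up to 21 days, which is longer than that margin. A response first seen at cycle 6 is confirmed on schedule at day 252, a gap of 252 − 183 = 69 days. That gives k = 14 / 11 and power 0.767 / 0.775 (f = 0.25) or 0.724 / 0.744 (f = 0.50).
- *12 months (day 365).* This passes day 336 by 29 days and allows on-schedule confirmation of responses first seen up to cycle 9 (252 + 84 = 336). A response first seen at cycle 12 could be confirmed only by a 4-week rescan (336 + 28 = 364).

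**The case against.** **The plan read as a whole points to a later cut.** Section 10.5.1 times the final analysis of the study, which includes PFS. PFS is to be evaluated 6 and 12 months after the last enrolment, and section 5 even lists it as a primary endpoint. The 3 cycles are only a minimum. This shows that a cut at the floor is not inevitable. It does not close the gap: the 6- and 12-month statements name PFS alone, and 10.5.1 does not refer to them.

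**A response seen on one scan is hardly *sustained*.** This is a reasonable reading and would remove the 4-week and worst-case rows for ORR. But the word is undefined, the reading still misses patients whose first response comes after cycle 3, and it does nothing for CBR. The CBR mismatch is the firmer half of the point.

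**The power figures stack assumptions.** They do. Accrual, response timing and a cut exactly at the floor are all assumed, as is the 84-day pause behind the 9-month figure. A longer pause would shorten the accrual window further and raise k. It is also argued that up to 62 patients enrol: keeping the threshold at 6, power would be 0.80–0.81 with rescans and 0.62–0.71 in the worst case. That spends the allowance for non-evaluable patients. With 39 in place of 33 in the step 1 formula, complete data on 62 would give power 0.837 and type I error 0.069, so a loss remains against the like-for-like figure.

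**The 6-month date would suffice.** It does meet both definitions, narrowly. Preferring 12 months is a judgement based on its margin.

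**Conclusion.** The concern holds. The mismatch between the 10.5.1 floor and the 10.4.1 definitions follows from the plan's own cycle length and scan schedule. For CBR it does not depend on how *sustained* is read. For ORR it holds unless *sustained* means confirmed and no response first appears after cycle 3.

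The size depends on accrual, response timing and when the cut is actually made. Only patients still ongoing at the cut are affected, mainly the last enrolled, and a later cut also satisfies 10.5.1. The power figures are therefore illustrations of what the rule permits, not forecasts. This should be fixed before the final analysis; it does not invalidate the design.

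**What to change.** Replace the 3-cycle minimum in 10.5.1 with wording such as: *The final analysis of ORR, CBR and PFS will use a data cut-off 12 months after the last patient is enrolled, or earlier only if every patient has progressed, died or ended follow-up. A response not confirmed by the cut-off is not counted in ORR and is listed separately.*

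Align the Primary Completion Date in section 12 and the 12-cycle statement in 10.5.2 with that cut-off. It would also help to state whether confirmation uses a 4-week rescan or the next scheduled scan. Appendix E allows either, so this is a clarification and the result does not depend on it.

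**Cost.** Two sentences in 10.5.1 and matching edits in section 12 and 10.5.2. The cut-off change needs no extra patients or visits. The ORR and CBR read-out would come up to 365 − 84 = 281 days (about 9 months) later than the floor allows, within follow-up already planned for PFS. If the 6-month date were chosen instead, the delay would be 183 − 84 = 99 days (about 3 months), with the narrower margin shown above.

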10.5.2 Planned Interim Analysis

No interim analyses are planned. Interim results may be presented at congress prior to final study report, if applicable. The design follows that of Simon et al. 1989. If < 2 of the initial 23 patients enrolled in the study fail to achieve a response, the study will be stopped and the remaining 33 additional patients will not be enrolled. Patients will be evaluated for response to treatment every 3 cycles. Patients will be removed from treatment at the time of disease progression. Patients demonstrating an extended period of stable disease will be considered non-responders after 12 cycles of treatment.

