10.2 Sample Size Considerations

This study will enroll up to 62 patients. Simon's optimal two-stage design (Simon, 1989) will be used for go/no go decision making. The null hypothesis that the true response rate is 0.05 will be *CONFIDENTIAL*

STUDY DRUG(S): CARFILZOMIB AMENDMENT 2 DATE: 25 FEBRUARY 2015

tested against a one-sided alternative. In the first stage, 23 patients will be accrued. If there is 1 or no response in these 23 patients, the study will be stopped. Otherwise, 33 additional patients will be accrued for a total of 56. The null hypothesis will be rejected if at least 6 responses are observed in 56 patients. This design yields a type I error rate of 0.05 and power of 80% when the true response rate is 0.15. The sample size will be increased by 10% to an accrual of 62 patients, to account for potential non-evaluability.

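### Section 10.5.2 counts non-responders where Section 10.2 counts responders, so the stage-1 futility rule is inverted, and it denies that any interim look is planned

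*Combined protocol and SAP*

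**What the plan says.** Section 10.2 sets out a Simon optimal two-stage design with 23 patients in stage 1, 33 more in stage 2, and rejection of the null at 6 or more responses in 56. Its stage-1 rule reads: "If there is 1 or no response in these 23 patients, the study will be stopped". It then states: "This design yields a type I error rate of 0.05 and power of 80% when the true response rate is 0.15".

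Section 10.5.2, headed Planned Interim Analysis, opens with "No interim analyses are planned". It cites the same Simon design and the same 23 + 33 split, but gives the rule as "If < 2 of the initial 23 patients enrolled in the study fail to achieve a response, the study will be stopped".

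Section 10.5.3 (Efficacy Review) is marked not applicable. Nothing in the document says which of the two sections governs.

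**The concern.** The two sections disagree on which stage-1 result ends the trial. Section 10.2 counts responders and stops when there are too few. Section 10.5.2 counts patients who do not respond and stops when there are too few of those, which means stopping for near-universal response and continuing after 0 or 1 responses. Both are current text.

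This is the only prespecified statistical stopping rule in a single-arm trial, and the stated type I error depends on it. Someone checking when to stop would naturally turn to 10.5.2, and would find the wrong count together with a statement that no look is planned. A rule with two incompatible readings also weakens any later claim that stopping, or continuing, followed the protocol.

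**Working it through.** **Inputs.** From Section 10.2: null rate p0 = 0.05 ("The null hypothesis that the true response rate is 0.05 will be" ... "tested against a one-sided alternative"), alternative p1 = 0.15, stage 1 n1 = 23, stop at 1 or fewer responses, stage 2 of 33, total 56, reject at 6 or more. From Section 10.5.2: stop if the number of non-responders, 23 − X1, is below 2, which is X1 ≥ 22. X1 is the number of stage-1 responders.

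**Step 1: reproduce the stated error rates with the 10.2 rule.** With Y ~ Bin(33, p),

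P(reject | p) = Σ (x = 2 to 23) C(23, x) p^x (1 − p)^(23 − x) × P(Y ≥ max(0, 6 − x)).

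This gives 0.04996 at p = 0.05 and 0.8003 at p = 0.15, matching the stated 0.05 and 80%. A search over designs with total size 20 to 69, for the smallest expected size under the null with type I error at most 0.05 and power at least 0.80, returns this same design. Section 10.2 is therefore internally sound.

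**Step 2: stopping behaviour of the 10.2 rule.**

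- P(stop | 0.05) = 0.95^23 + 23 × 0.05 × 0.95^22 = 0.30736 + 0.37206 = 0.6794.
- P(stop | 0.15) = 0.1204, by the same formula.
- E[N | 0.05] = 23 + (1 − 0.6794) × 33 = 23 + 0.3206 × 33 = 33.58.

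**Step 3: the 10.5.2 rule as written.**

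P(stop | p) = P(X1 ≥ 22) = 23 p^22 (1 − p) + p^23, which is about 5.2 × 10^−28 at p = 0.05 and 1.5 × 10^−17 at p = 0.15. The trial then always runs to 56 for practical purposes, and the test reduces to P(X ≥ 6) with X ~ Bin(56, p).

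| | 10.2 rule | 10.5.2 read literally |
|---|---|---|
| P(stop at stage 1), p = 0.05 | 0.679 | about 5 × 10^−28 |
| P(stop at stage 1), p = 0.15 | 0.120 | about 1.5 × 10^−17 |
| Type I error | 0.04996 | 0.0602 |
| Power at 0.15 | 0.8003 | 0.8638 |
| Expected evaluable N, p = 0.05 | 33.6 | 56.0 |

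**Step 4: patients at stake under the null.** The difference is 0.6794 × 33 = 22.4 evaluable patients if accrual pauses at 23. The documents state no pause, and a stage-1 result takes time to mature. Section 10.5.2 says "Patients will be evaluated for response to treatment every 3 cycles", so with 28-day cycles the first scheduled reading is at about 3 × 28 = 84 days. Section 10.4.1 requires "2 CRs or PRs at least 4 weeks apart", so confirmation comes at about 84 + 28 = 112 days at the earliest on that schedule. If k patients enrol in the meantime, the difference is 0.6794 × (33 − k). For assumed values of k:

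- k = 10: 0.6794 × 23 = 15.6
- k = 20: 0.6794 × 13 = 8.8

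**The case against.** The strongest reply is that nobody would be misled. Section 10.2 gives the rule without ambiguity and with every design parameter. Section 10.5.2 cites the same design and sample sizes. A rule that stops a trial for 22 responses in 23, when the hypotheses are 5% and 15%, cannot be taken for a futility rule. On this view the inflated type I error and the extra patients are hypothetical, because they arise only if staff disregard 10.2.

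That is fair as far as it goes. The error is one of wording, not of method, and the figures for the literal reading are conditional. It does not remove the conflict: the section that carries the stopping rule states it wrongly, and no text ranks one section above the other.

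A second reply is that a Simon stage-1 gate need not be called an interim analysis, so the opening sentence of 10.5.2 may mean only that nothing beyond that gate is planned. This reading is reasonable, since both sections do describe the look. This part is a clarification and would not justify a required change alone.

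A third point also stands. The 10.2 stage-1 rule is necessary for the stated error rates but not sufficient. They also assume exactly 23 and 56 evaluable patients, whereas Section 10.2 allows accrual of 62 and Section 10.4.1 reports efficacy on the Full Analysis Set. That is a separate matter and does not affect which stage-1 rule is correct.

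**Conclusion.** The concern holds and the text must be corrected. Section 10.5.2 swaps non-responders for responders in the stage-1 rule, and the plan's own error rates identify 10.2 as the intended version. The severity rests on the contradiction sitting in the sole go/no-go rule, not on any likelihood that the literal wording would be carried out.

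The numerical consequences apply only if 10.5.2 were followed instead of 10.2: the futility stop disappears in effect and type I error exceeds the stated 0.05. They assume a true rate of exactly 5% or 15% and independent responses. The loss of 22.4 patients further assumes an accrual pause at 23, and it shrinks with overrun as shown in Step 4.

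**What to change.** Change two sentences in Section 10.5.2.

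1. Replace the stopping sentence with: *The trial stops for futility if fewer than 2 (that is, 0 or 1) of the first 23 patients achieve a response; in that case the 33 stage-2 patients are not accrued.*
2. Replace the opening statement with: *One futility look is planned, at the end of stage 1, as described in Section 10.2; there is no stopping for efficacy.*

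The cost is protocol wording only. Design, sample size, budget and timelines stay as Section 10.2 already requires, and patients are not affected.
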